### **Analysis Inclusion**

Only those who meet eligibility criteria will be included in the final analysis. Specific outcome measures will be ascertained only in patients who complete follow-up questionnaires, as indicated.

### **Missing Data**

Data imputation will not be used for missing data.

## **Harms**

Serious adverse events and non-serious adverse events resulting in emergency department visits will be collected up until 1 year following the initial consult appointment.

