## Scientific Background

Laryngomalacia (LM) is the most common cause of stridor in infants. Symptoms of gastroesophageal reflux (GER) are often seen in the setting of LM; therefore, acid suppression therapy (AST) has been empirically used in the management of this disorder. Our team recently performed a retrospective chart review assessing improvement of airway and dysphagia symptoms, weight gain, and need for surgery with AST. We have found that there was a similar improvement between LM severity groups and the majority of patients received AST. It is unclear if these improvements are due to AST or natural resolution of the disease. With heightened concerns of side effects related to AST in infants, particularly among those born prematurely, judicious use of these medications is needed. We are now performing a prospective study looking at the outcome differences in patients with laryngomalacia who are evaluated by speech language therapy (SLP) alone versus those with SLP evaluation and AST. There is no gold standard in treating mild and moderate LM patients and therefore this study would help establish these guidelines.

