These patients will then be re-evaluated at their follow up appointment in 1 to 4 months. The families will take the PASS and I-GERQ-R surveys again to determine LM severity. If Pepcid is discontinued due to intolerance of side effects, they will be kept in the study in the same arm. If the family opts out of the follow-up appointment or they do not need to follow-up in-person, families will take the post surveys via REDCap or by mail. A REDCap link will be sent along with a letter to the caregivers to the caregivers' email address on file. If the families do not fill out the surveys within 2 weeks, paper copies of the surveys along with a letter to the caregivers will be sent to the caregivers' home address on file. If the families do not return the paper copy or the electronic copy of the surveys, researchers will call the participants for a reminder and will ask if the family wants another paper copy or survey link. The family may also answer the survey questions over the phone.

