## Secondary Outcomes

- Weight (kg) From Consult up to 1 Year.
  - Weight change in kilograms assessed from medical chart review from consult up to 1 year
- Number of Participants With the Need for Supraglottoplasty Surgery (Escalation of Treatment) up to 1 Year.
  - The need for escalation of treatment with supraglottoplasty surgery will be assessed through medical chart review up to 1 year.

- Number of Participants With the Need for Acid Suppression Therapy Medication (Famotidine) From Speech Language Therapy Alone Group From the Day After the Consult up to the 3 Month Follow up Appointment.
  - The speech language therapy alone group will be assessed for the need for a prescription for acid suppression therapy (famotidine) from the day after the consult up to 1 year.
- Number of Participants With Each Type of Laryngomalacia (Types 1-3) Found on the Flexible Laryngoscopy Procedure at the Consult.
  - All patients will be scoped with a flexible laryngoscopy at the initial consult and the type of laryngomalacia (Types 1-3) will be noted.
- Number of Participants With the Need for a Different Acid Suppression Therapy Medication (Other Than Famotidine) From the Day After the Consult up to the 3 Month Follow up Appointment.
  - Both groups will be assessed for the need for a different acid suppression therapy medication (other than famotidine) from the day after the consult up to the 3 month follow up appointment.

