### **Cross-Over**

Intent-to-treat analysis will be performed.

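### Non-serious intolerance that leads a family to stop famotidine falls outside the harms rule, and the documents do not say that such stops will be recorded or reported.

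*Combined protocol and SAP*

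**What the plan says.** The Harms section of the combined protocol and SAP is a single sentence: "Serious adverse events and non-serious adverse events resulting in emergency department visits will be collected up until 1 year following the initial consult appointment". A serious event counts whether or not there is an emergency visit. A non-serious event counts only if there is one, the operative words being "non-serious adverse events resulting in emergency department visits will be collected".

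The follow-up part of Methods foresees treatment being stopped for tolerability: "If Pepcid is discontinued due to intolerance of side effects, they will be kept in the study in the same arm". It settles which arm the infant belongs to. It does not say that the stop, its date or its reason is captured.

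Scientific Background gives two reasons for the study. One is doubt about benefit: "It is unclear if these improvements are due to AST or natural resolution of the disease". The other is safety: "With heightened concerns of side effects related to AST in infants, particularly among those born prematurely, judicious use of these medications is needed".

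The closest listed outcome is under Secondary Outcomes: "Both groups will be assessed for the need for a different acid suppression therapy medication (other than famotidine) from the day after the consult". It runs to the 3 month follow-up. On cross-over, the plan says "Intent-to-treat analysis will be performed". The Analyses section describes no comparison of adverse events.

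**The concern.** The plan names a drug-related event that it expects, and sets a harms rule too narrow to include it when it is non-serious and does not lead to an emergency visit. This is a stated restriction, so a team that follows the plan as written could produce a harms table with no tolerability data at all.

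Two things are at stake. First, the study hypothesises no difference in outcomes and hopes to help establish guidelines for mild and moderate laryngomalacia. If the arms look alike on symptoms, tolerability becomes a large part of whether acid suppression is worth giving, and that part would be thin. Second, infants who stop stay in the famotidine arm under intent-to-treat. That is the right analysis set, but without a count of stops a reader cannot tell whether a null result reflects a drug that does not help or one that was often not taken.

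**Working it through.** The plan states no figure on this point, so there is nothing to reproduce. The check has two parts.

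**1. Is the event captured anywhere?** Take an infant in the famotidine arm whose family stops the drug for a non-serious side effect, with no emergency visit.

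| Section | Would it record this infant's stop? |
|---|---|
| Harms | No: neither serious nor an emergency visit |
| Methods (follow-up) | Keeps the infant in the arm; mentions no recording |
| Primary Outcome | No: symptom scores and chart-reviewed airway and dysphagia symptoms |
| Secondary Outcomes | Only if another acid suppressant is needed by the 3 month visit, and then not as a harm |
| Analyses, Cross-Over, Analysis Inclusion, Missing Data | No discontinuation, tolerability or adverse-event analysis |

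Secondary Outcomes does count infants in the speech-therapy-alone arm who come to need famotidine. The plan thus tracks entry to the drug in one arm but not exit from it in the other.

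**2. How many infants might this involve?** The inputs are:
- n = 80 infants planned for the famotidine arm (Sample Size Calculation).
- d, the proportion stopping for non-serious side effects. The documents give none, so 5–15% is an assumption for scale.
- e, the share of those stops that also involve an emergency visit. This is also assumed: 0, 10% or 25%.

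Expected stops = n × d. Expected number recorded under the present rule = n × d × e.

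| d | Stops | Recorded, e = 0 | Recorded, e = 10% | Recorded, e = 25% |
|---|---|---|---|---|
| 5% | 80 × 0.05 = 4 | 0 | 4 × 0.10 = 0.4 | 4 × 0.25 = 1 |
| 10% | 80 × 0.10 = 8 | 0 | 8 × 0.10 = 0.8 | 8 × 0.25 = 2 |
| 15% | 80 × 0.15 = 12 | 0 | 12 × 0.10 = 1.2 | 12 × 0.25 = 3 |

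The e = 0 column is zero by construction. It shows what the rule does and is not evidence about famotidine.

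A zero in the table could also be misread. With 0 events in 80, the one-sided exact 95% upper bound is 1 − 0.05^(1/80) = 0.0368, or 3.7%. A reader who took that zero as covering all intolerance would think rates above 3.7% excluded, while 4 to 12 infants (5–15%) might have stopped. With 62 infants, the number per group that the plan says it needs before allowing for attrition, the same rates give 62 × 0.05 = 3.1 to 62 × 0.15 = 9.3 stops.

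**The case against.** The case for leaving the rule alone has substance. Methods describes both treatments as standard of care, so targeted harms collection is defensible. No placebo or blinding is described, and an emergency-visit threshold is less open than minor complaints to families and clinicians reporting more on the arm they know receives a drug. Several measures that might reflect poor tolerability are taken in both arms regardless of emergency visits: emesis after feeds, choking, coughing and gagging, the I-GERQ-R, weight, and need for another acid suppressant. All of this stands. None of these measures is labelled a harm, however, and none counts a stop or gives its reason.

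A reader might infer more than the documents support:

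- *That stops will go unrecorded.* The text does not say so. The rule for keeping such infants in their arm presupposes that staff learn of the stop and why. What can be said is that no section commits to recording or reporting it.
- *That every intolerance without an emergency visit is lost.* Serious events are collected either way. The gap is non-serious intolerance only.
- *That side effects are the motive for the trial.* They are one of two, beside uncertain benefit. The safety sentence stresses infants born prematurely, whom the Exclusion list removes, and the aim and hypothesis do not mention safety.
- *That the commonest harms of famotidine are left out.* The documents give no side-effect profile and no frequencies.
- *That stopping should be compared between arms.* The control arm is not assigned famotidine, so a risk difference for stopping it would mean little.

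**Conclusion.** The point holds within those limits. The Harms rule does not cover non-serious intolerance without an emergency visit, Methods foresees such intolerance leading families to stop famotidine, and no outcome or analysis makes up the difference. In a study partly motivated by concern about side effects and meant to inform guidelines, this weakens the benefit–harm conclusion. It leaves the primary analysis intact, exposes no wrong figure or test, and involves no contradiction between sections. It is a worthwhile improvement and not a serious flaw.

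The size cannot be fixed from the documents. Assuming that 5–15% of 80 infants stop, it is 4–12 infants, uncaptured unless the event is serious or leads to an emergency visit. Some may show indirectly as a switch to another drug. Stops among infants lost to follow-up might not be learned of under any rule.

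**What to change.** Extend the Harms section. The change concerns data collection only and alters no treatment rule.

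1. Record each famotidine discontinuation with its date and reason. Report it as a count and proportion with a 95% CI in the famotidine arm alone, and state how many infants had follow-up information.
2. Collect non-serious adverse events in both arms from two sources: the otolaryngology notes already reviewed to 1 year, and one question added to the follow-up survey, worded identically in both arms and for every route (clinic, REDCap, mail or phone). The question is needed because families may skip the in-person visit and then have no follow-up note to review.
3. Report adverse events by arm with risk differences and 95% CIs, keeping serious events and emergency visits as separate rows so that the measure less open to reporting bias remains visible.

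The cost is a few more abstraction fields and one survey question. The main downside is that, with no blinding described, minor events may be reported more often in the drug arm. The report should state this as a limitation.
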